5.6.6. Vital Signs

The analyses described below will be conducted for the following vital signs assessments respectively:

- SBP (mmHg);
- DBP (mmHg);
- Heart rate (bpm);
- Body Temperature ($^{\circ}\text{C}$)

The following will be summarized by overall for the ASaT population:

- Observed values and change from baseline at each scheduled assessed visit for each standard vital sign parameter using default summary statistics for continuous variables

A listing of all vital signs data including derived change from baseline will be provided for the screened population.

The actual values and CFB for each scheduled study visit for selected vital signs parameters will be plotted at each time point using a line plot including 95% CI bars around the mean, this will be done by overall for ASaT population.

Total counts and percentages of patients will be presented for the following:

- Maximum increase from baseline in SBP and DBP (mmHg):
 - <20
 - ≥ 20 and <40
 - ≥ 40 and <60
 - ≥ 60
- Maximum decrease from baseline in SBP and DBP (mmHg):
 - <20
 - ≥ 20 and <40
 - ≥ 40 and <60
 - ≥ 60
- Maximum increase from baseline in heart rate (bmp):
 - <30
 - ≥ 30
- Maximum decrease from baseline in heart rate (bmp):
 - <30
 - ≥ 30
- Maximum postdose heart rate (bmp)
 - <50
 - ≥ 50 and <120
 - ≥ 120

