8.2.3 Special assessments on treatment days

8.2.3.1 Nanrilefusp alfa treatment days of cycles 1 to 3

Patients will be observed in the hospital up to 4 hours following nanrilefusp alfa administration. Vital signs (blood pressure [systolic and diastolic, after ≥ 5 minutes of rest], body temperature, and heart rate) will be documented at the following frequency until discharge:

- Before nanrilefusp alfa administration
- 15 minutes (± 5 minutes) after nanrilefusp alfa administration
- 30 minutes (± 5 minutes) after nanrilefusp alfa administration
- 2 hours (± 15 minutes) after nanrilefusp alfa administration
- 4 hours (± 30 minutes) after nanrilefusp alfa administration

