4.1.4. Visit Windows

All data will be analyzed using nominal study visit as defined in the Study Schedule and eCRF. No visit windows will be applied for summary and analysis except for tumor assessment. Repeated and unscheduled measurements will be included in the listings but not be used for statistical analyses and summaries, except for the derivation of minimum/maximum values post-baseline. All tumor assessments will be considered for the time-to-event analysis.

Unscheduled visits will be identified with a numbering system that reflects the cycle they occur in by comparing the visit date against the scheduled visits and numbering in order of unscheduled visit e.g. Unscheduled Cycle 1 Day 1.01, Unscheduled Cycle 1 Day 8.01 etc. Unscheduled visits occurring on the same day as other visits will not be used in the analysis by timepoint.

Visit window for the Tumor Assessment

Additionally, for the purposes of summarizing target lesions by scheduled week, labels for assessments falling into the scheduled week of study will be derived e.g. ‘Week 6 assessment (Weeks 4 to 8)’, ‘Week 12 assessment (Weeks 10 to 14)’ etc., by assigning the assessments within the protocol specified window of every 6 weeks \pm 2 weeks (e.g. for Week 6 : C1D1 date + 28 \leq Tumor assessment date \leq C1D1 date + 56). Labels for assessments falling outside of the assessment windows would be labelled ‘Not Assigned’. In the case of multiple tumor assessments in a time window, evaluable assessments closest to the planned assessment time (or the closest non-evaluable assessment if all non-evaluable) will be considered the scheduled assessment. In the case of two assessments within a window being exactly the same distance from the centre of the window, the earliest assessment will be assigned as the scheduled assessment. Contributing assessments (e.g. target lesion assessment) should be labelled consistently with the overall tumor assessment.

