5.1. General Principles

All data processing, summarization and analyses will be performed using Fortrea's SAS Environment / Version 9.4 (or later) of the SAS® statistical software package.

The analyses will be descriptive; no formal testing of statistical hypotheses is planned.

Summary statistics:

The default summary statistics for quantitative variables will be the number of observations (n), mean, Standard Deviation (SD), median, minimum (min) and maximum (max), for those patients with data. For qualitative variables, the number (n) and percentage (%) of patients with non-missing data per category will be the default summary presentation, and where appropriate and present, the number of missing values as a "Missing" category. Number of patients in the analysis population will be used as denominator for percentages calculation, unless stated otherwise in TFLs.

Time-to-event endpoints will be summarized using Kaplan-Meier (KM) method. Estimation of median time and the associated 95% Confidence Interval (CI) will be provided using log-log transformation. Number of events, number of censored patients and descriptive statistics [25th and 75th percentiles, minimum and maximum] for time-to-event endpoints will be also provided. The KM curves will be graphically displayed.

Time conversion:

The following conversion factors will be used to convert days into months or years:

1 week = 7 days, 1 month = 30.4375 days, 1 year = 365.25 days.

Laboratory data:

All laboratory clinical safety and urine test results will be received from the local laboratories, and the results will be provided in both Standard Internal (SI) and conventional units. For the TFLs, the results will be summarized or presented in International System of Units (SI) units. Refer to Appendix of the TFLs mock shells for the SI unit corresponding to each laboratory test. Biomarkers, inflammatory cytokines and PK/ADA results will be received from the central laboratories.

Tables, Figures, and Listings (TFLs):

In the listings, laboratory values converted from conventional to International System of Units (SI) units will be reported to the same precision as values originally recorded as SI. Derived values for change/ percent changes in target lesions, and all safety endpoints will be rounded with one decimal place.

Refer to Appendix of the TFL shells for the precision level in which each laboratory test is reported by the central laboratories.

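### SAP 5.6.6 applies the <50 category to the maximum post-dose heart rate, so the table gives no valid count of patients with any post-dose rate below 50

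*SAP*

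**What the plan says.** SAP 5.6.6 (Vital Signs) lists categorical summaries as counts and percentages of patients. Two of them bear on low heart rates:

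- "Maximum postdose heart rate (bmp" with bands <50, ≥50 and <120, and ≥120.
- "Maximum decrease from baseline in heart rate (bmp" with bands <30 and ≥30.

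There is no row for the minimum post-dose heart rate.

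The same section plans "Observed values and change from baseline at each scheduled assessed visit for each standard vital sign parameter". The default statistics in SAP 5.1 include "median, minimum (min) and maximum (max". It also states: "A listing of all vital signs data including derived change from baseline will be provided for the screened population".

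SAP 4.1.4 keeps repeated and unscheduled measurements out of the summaries, "except for the derivation of minimum/maximum values post-baseline".

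The reading schedule is in Protocol 8.2.3. For cycles 1 to 3, "Patients will be observed in the hospital up to 4 hours following nanrilefusp alfa administration", with vital signs, including heart rate, at 15 minutes, 30 minutes, 2 hours and 4 hours after the injection. From cycle 4 the 4-hour reading is dropped.

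**The concern.** A low cut-point belongs with a minimum and a high cut-point with a maximum. Here both are attached to the maximum. The row labelled <50 then answers whether the patient's heart rate was below 50 at every post-dose reading. A safety reader would want to know whether it was below 50 at any of them.

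Putting both ends in one three-way classification adds a second problem. A patient can have a low excursion and a high one, but can sit in only one band, and the maximum decides which.

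Vital signs are a named secondary safety endpoint (Protocol section 3), and Protocol 9.3.3.2 commits to summarizing them. What is at stake is whether the categorical summary gives a usable count of patients with low post-dose heart rates.

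**Working it through.** **Inputs.** Bands: SAP 5.6.6. Readings: Protocol 8.2.3, with nanrilkefusp alfa on days 1, 2, 8 and 9 of each cycle (Protocol 6.1). SAP 5.6.6 does not define post-dose, so I take it to mean the scheduled readings after each injection.

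**Number of readings behind the maximum.**
- Cycle 1: 4 time points × 4 dosing days = 16.
- Cycles 1 to 3: 16 × 3 = 48.
- Each cycle from cycle 4: 3 × 4 = 12.

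**Logic.** For one patient's readings x1, …, xn:
- max(x1, …, xn) < 50 if and only if all n readings are below 50.
- At least one reading is below 50 if and only if min(x1, …, xn) < 50.

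Because min ≤ max, every patient in the SAP's <50 row also has a minimum below 50, but the converse fails. The row can therefore only equal or understate the number of patients with any reading below 50.

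**Illustrative patients** (values invented to test the rows):

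| Baseline | Post-dose readings | Maximum and its band | Minimum | Largest fall and its band |
|---|---|---|---|---|
| 70 | 72, 64, 42, 68 | 72: ≥50 and <120 | 42 | 70 − 42 = 28: <30 |
| 78 | 80, 49, 60, 75 | 80: ≥50 and <120 | 49 | 78 − 49 = 29: <30 |
| 70 | fifteen of 48, one of 50 | 50: ≥50 and <120 | 48 | 70 − 48 = 22: <30 |
| 90 | 92, 85, 45, 88 | 92: ≥50 and <120 | 45 | 90 − 45 = 45: ≥30 |
| 58 | 48, 47, 46, 49 | 49: <50 | 46 | 58 − 46 = 12: <30 |
| 115 | 112, 90, 80, 100 | 112: ≥50 and <120 | 80 | 115 − 80 = 35: ≥30 |

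The first three patients have a rate below 50 that neither row picks out. The fourth is missed by the maximum row and caught by the decrease row. The fifth is counted as <50 because all of the readings are low. The sixth is flagged for a large fall without ever being near 50. In addition, a patient with a nadir of 40 and a peak of 130 is counted only as ≥120.

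**When the decrease row misses a low nadir.** With baseline B and nadir m, the fall is below 30 when B − m < 30, that is, when B < m + 30:
- m = 49: missed if B is below 79.
- m = 45: missed if B is below 75.
- m = 40: missed if B is below 70.

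**Other planned outputs.**
- The by-visit minimum is the lowest value in the group at that visit. It does not say how many patients were below 50 at any time.
- The listing shows each value but counts nothing.
- ECG heart rate is listed only (SAP 5.6.8).
- Protocol 8.3.8.1 asks for a vital-sign abnormality to be recorded as an adverse event only if it is clinically relevant, so the adverse event tables count something narrower.
- Under SAP 4.1.4 an unscheduled reading enters the summaries only through a post-baseline minimum or maximum. An unscheduled reading of 42 with a fall below 30, in a patient whose other readings are higher, is identified by no vital-sign summary and appears only in the listing.

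**The case against.** The strongest reply is that low heart rates are not hidden. A patient who is below 50 throughout is counted in the <50 row. The ≥30 decrease row catches some large falls. Scheduled low values show in the by-visit minima, every value is listed, and clinically relevant bradycardia should reach the adverse event tables. The analyses are descriptive, and neither the dose-limiting toxicity definition nor the futility rule uses this row. The row also carries its own label, so an attentive reader can see that it concerns a maximum. Detailed table formats sit in shells that are not part of these documents.

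Most of this stands, and it rules out three stronger readings that a reader might infer:

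- That the trial cannot detect bradycardia. It can, through the routes just named.
- That a patient with a low nadir is counted as normal. The SAP gives the middle band no such label.
- That a near-empty <50 row will be taken to mean no bradycardia. That is a guess about readers, which the documents do not settle.

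The reply does not supply the missing number. None of these outputs counts patients with any post-dose rate below 50, and the only row with that cut-point counts something else. The shells might differ, but the SAP text as written does not provide the count.

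**Conclusion.** The point holds as a minor error in a descriptive safety table. As written, the <50 row counts only patients whose every post-dose reading is below 50, and anyone who also peaks at 120 or more appears only in the top band. The direction of the error is certain, because the row cannot overstate the number with any reading below 50. Its size is not computable, because the documents give no frequency of low readings. A figure would need an assumed rate per reading and an assumption about how readings within a patient are related.

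The conclusion assumes that the maximum is taken per patient over all post-dose readings, as a table of patient counts implies. If it were taken per dosing day, the same flaw would apply, with 4 readings (3 from cycle 4) needing to be below 50. The primary endpoint, the sample size and the stopping rule are untouched.

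**What to change.** In SAP 5.6.6, replace the single three-band block with two blocks that keep the existing cut-points:

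- Minimum post-dose heart rate: <50, ≥50.
- Maximum post-dose heart rate: <120, ≥120.

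State which readings count as post-dose and that unscheduled readings are included, in line with SAP 4.1.4. Correct the unit from bmp to bpm in the heart-rate rows, and carry the change into the table shells.

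The cost is one extra row block. No new data are needed, and SAP 4.1.4 already foresees deriving post-baseline minima.

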5.6.7. Body Surface Area

The analyses described below will be conducted for the following BSA assessments respectively:

- Height (cm);
- Weight (kg);
- Body Surface Area (m^2)

A listing of all body surface area data including derived change from baseline will be provided for the screened population.

5.6.8. Electrocardiograms

The following ECG assessments will be taken during the study:

- An overall investigator assessment classified as normal / abnormal, not clinically significant / abnormal, clinically significant / unevaluable / unknown
- Heart rate (bpm);
- PR interval (msec);
- QRS interval (msec);
- QT interval (msec);

- Bazett Corrected QT (QTcB) interval (msec);
- Fridericia Corrected QT (QTcF) interval (msec)

A listing of all ECG data will be provided for the screened population.

5.6.9. Left Ventricular Ejection Fraction (LVEF)

LVEF data will be listed for ASaT population.

5.6.10. Physical Examination

Physical examination data will be listed for each patient at each assessed visit for the screened population.

5.6.11. Other Safety Variables

5.6.11.1. Eastern Cooperative Oncology Group (ECOG)

Total counts and percentages of patients will be presented for the ECOG performance status scores on the ASaT population.

ECOG performance status scores will be listed for each patient at each assessed visit for the ASaT population.

5.6.11.2. Pregnancy Test

Pregnancy test results will be listed for each patient at each assessed visit for the screened population.

5.6.12. Interim Analysis and Data Monitoring

An analysis for futility will be performed when the sample size is considered enough for such analysis. Efficacy data and outputs will also be a part of the IDMC review.

The futility analysis will be conducted once all patients in the efficacy population planned for futility analysis will have post-baseline tumor assessment data or discontinue the treatment before the post-baseline assessment. Patients in efficacy population who discontinue and have no evaluable post-baseline tumor assessment available will be considered as non-responders.

Assuming a desired ORR, the futility analysis will be based on a comparison against a minimal ORR considered as both statistically and clinically relevant improvement as compared to the benchmark ORR. An 80% CI using the exact method for the ORR (alpha = 0.2, alpha = 0.1 one-sided) will be used. The analysis will be based on the efficacy population.

If the ORR is:

- lower than the minimal ORR, and
- the 80% CI for the ORR does not include the minimal ORR,

It will be concluded that the combination treatment is futile as compared to cetuximab treatment alone and thus the study will be discontinued. However, patients still on treatment can continue combination therapy if recommended by the IDMC.

The criteria for conclusion of futility are defined as follows:

- Benchmark ORR = 20%; minimal ORR = 28.8%; desired ORR = 36.8%
- N = 16 patients if the number of responses is less than 2 ($r < 2$)

Additionally, the ORR will be evaluated on an ongoing basis (without stopping of recruitment). Other efficacy endpoints will be used as supportive information.

For the purposes of interim analyses, in the case of ongoing patients with any unconfirmed response and for whom a confirmatory scan is still pending:

- Responders (PR, CR) or patients with SD that, at the time of the futility analysis, did not yet have a second (confirmatory) tumor assessment performed will be considered to have an Unconfirmed response (PR, CR) or Unconfirmed SD as BOR, respectively. Such BORs will be presented with “Unconfirmed” label.
- ORR will also include Unconfirmed PR and Unconfirmed CR in the numerator.

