8.1.2 Tumor imaging during the study

The first on-study scan assessment should be performed at 6 weeks (± 2 weeks; starting from cycle 1 day 1). Subsequent tumor scans should be performed every 6 weeks (± 2 weeks).

All supplemental imaging must be collected.

Objective response should be confirmed by repeat scan performed at least 4 weeks after the first indication of a response is observed. Patients will then return to the regular scan scheduled, starting with the next scheduled time point. Patients who receive additional scans for confirmation do not need to undergo the next scheduled scan if it is fewer than 4 weeks later; scans may resume at the subsequent scheduled time point.

When radiological disease progression is identified by the investigator in clinically stable patients, disease progression is to be confirmed by another set of scans performed 4 to 8 weeks later, per iRECIST guidelines in section [8.1.5](#).

If disease progression is not confirmed, clinically stable patients are to continue study interventions until progression is confirmed. Patients are to return to their regular scan schedule. If the next scheduled scan will occur in less than 4 weeks, this scheduled scan may be skipped.

If disease progression is confirmed, study interventions will be discontinued. Exceptions are detailed in section [8.1.5](#).

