9.4 Interim analysis

An analysis for futility will be performed when the sample size is considered enough for such analysis. Efficacy data and outputs will also be a part of the IDMC review.

Assuming a desired ORR, the futility analysis will be based on a comparison against a minimal ORR considered as both statistically and clinically relevant improvement as compared to the benchmark ORR. An 80% CI using the exact method²⁶ for the ORR (alpha = 0.2, alpha = 0.1 one-sided) will be used.

The analysis will be based on the efficacy population.

If the ORR is:

1. lower than the minimal ORR, and
2. the 80% CI for the ORR does not include the minimal ORR,

it will be concluded that the combination treatment is futile as compared to cetuximab treatment alone and thus the study will be discontinued. However, patients still on treatment can continue combination therapy if recommended by the IDMC.

The criteria for conclusion of futility are defined as follows:

- Benchmark ORR = 20%²¹; minimal ORR = 28.8%; desired ORR = 36.8%
- N = 16 patients if the number of responses is less than 2 (r < 2)

Additionally, the ORR will be evaluated on an ongoing basis (without stopping of recruitment). Other efficacy endpoints will be used as supportive information.

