5.5.3. Secondary Efficacy Analysis

5.5.3.1. BOR and iBOR

The BOR and iBOR are defined as the best response from the start of study treatment until the first documented disease progression, death, or start of new anti-cancer therapy. It will be summarized with counts and percentages in the efficacy population and will be repeated for ASaT and PP populations.

This will also be repeated in the efficacy population where patients with missing data will be excluded from the analysis.

Stable Disease according to RECIST 1.1 (SD) and Stable Disease according to iRECIST (iSD) needs to last at least 6 weeks from the start of study treatment, if not, at least one follow-up scan is required to declare stable disease.

BOR according to RECIST and iRECIST as well as the Overall Response will also be listed for enrolled population.

For BOR each patient will be assigned one of the following categories (from best response to worst response): CR, PR, SD, PD, NE:

Step	Condition
Step 1: BOR of CR If a BOR of CR is not determined, Step 2 will be performed.	At least two consecutive determinations of CR more than 4 weeks apart, or if not consecutive, with no other assessment between the two determinations other than unable to evaluate (NE), CR.
Step 2: BOR of PR If a BOR of PR is not determined, Step 3 will be performed.	At least two consecutive determinations of PR or CR, more than 4 weeks apart, or if not consecutive, with no other assessment between the two determinations other than NE, CR, PR.
Step 3: BOR of SD If a BOR of SD is not determined, Step 4 will be performed.	At least one SD assessment (or better), ≥ 6 weeks (≥ 42 days) after baseline; if not, at least one follow-up scan (i.e., consecutive scan) evaluated as SD (or better) is required

	to determine a BOR of SD. If not consecutive scans, with no other assessment between the two determinations other than NE, CR, PR, SD.
Step 4: BOR of PD If a BOR of PD is not determined, Step 5 will be performed.	At least one (i.e., any) PD after baseline.
Step 5: BOR of NE	Measurable disease at baseline, but not all or any target lesions have been evaluated, or if derivation of BOR from Step 1 to 5 does not apply. Non-measurable disease at baseline will also result in BOR of NE.

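### The futility look has no minimum follow-up, so late-enrolled patients with a single scan who would respond later count as non-responders against a whole-course ORR threshold

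*SAP*

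**What the plan says.** - **When the look opens (SAP 5.6.12).** "The futility analysis will be conducted once all patients in the efficacy population planned for futility analysis will have post-baseline tumor assessment data", or have discontinued treatment before that assessment. Protocol 9.4 leaves the timing to a judgement that there are enough patients and adds no follow-up requirement.
- **The boundary (SAP 5.6.12).** Futility is set at "N = 16 patients if the number of responses is less than 2". It comes from comparing the observed ORR with the minimal ORR of 28.8%: "An 80% CI using the exact method for the ORR (alpha = 0.2, alpha = 0.1 one-sided) will be used".
- **The consequence (Protocol 9.4).** If the boundary is crossed, "it will be concluded that the combination treatment is futile as compared to cetuximab treatment alone and thus the study will be discontinued".
- **The scans (Protocol 8.1.2).** "The first on-study scan assessment should be performed at 6 weeks", with a window of ±2 weeks, so the first scan can fall at week 4. After that, "Subsequent tumor scans should be performed every 6 weeks", which puts the second at about week 12.
- **The endpoint (SAP 5.5.1 and 5.5.3.1).** ORR is derived from best overall response, which is the "best response from the start of study treatment until the first documented disease progression, death, or start of new anti-cancer therapy".
- **Pending data at the look (SAP 5.6.12).** Unconfirmed PR and CR go into the numerator. Patients with stable disease and no second scan are labelled as unconfirmed SD. No allowance is made for a first response that has not yet appeared.

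**The concern.** The threshold and the count are measured over different periods. The 28.8% is a rate of best response over the whole course, and the same benchmark, minimal and desired rates size the 52-patient analysis (Protocol 9.5, SAP 2.3). The count at the look is best response to date, and for the last patients enrolled that can mean one scan. Such a patient with stable disease is still on treatment and able to respond, yet sits in the denominator as a failure.

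The SAP deals with half of this: a pending confirmation is credited, a pending first response is not. Missing later first responses can only lower the count. Because the rule is worded as a stop, the risk is that an active combination is abandoned on immature data.

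**Working it through.** **Inputs**
- N = 16, stop at 0 or 1 responses; 80% exact interval; minimal ORR 28.8%, desired ORR 36.8% (SAP 5.6.12, Protocol 9.4).
- First scan week 6 ±2, second about week 12 (Protocol 8.1.2).
- f = share of eventual responses visible at the first scan. Not in the documents; assumed 0.5 to 0.7.
- m = number of the 16 whose responses are all visible at the look (called mature). Also an assumption: 6 as the main case, with 0, 3 and 9 for range.

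**Step 1: the plan's boundary.** The upper limit of the 80% Clopper-Pearson interval for x of 16 is the 90th percentile of Beta(x+1, 16−x).
- x = 1: 22.2%, below 28.8%, so stop.
- x = 2: 30.0%, above 28.8%, so continue.

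The stated rule, fewer than 2 of 16, is reproduced.

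**Step 2: mature data.** P(stop) = (1−p)^16 + 16p(1−p)^15.
- p = 0.368: 0.00065 + 0.00604 = 0.0067 (0.7%).
- p = 0.288: 0.00436 + 0.02823 = 0.0326 (3.3%).

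**Step 3: six mature patients, ten with the first scan only.** Let a0 = (1−p)^6, a1 = 6p(1−p)^5, b0 = (1−pf)^10, b1 = 10pf(1−pf)^9. Then P(stop) = a0·b0 + a1·b0 + a0·b1.

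| p | f | pf | a0 | a1 | b0 | b1 | P(stop) |
|---|---|---|---|---|---|---|---|
| 0.368 | 0.7 | 0.2576 | 0.0637 | 0.2226 | 0.0509 | 0.1765 | 0.00324 + 0.01132 + 0.01125 = 2.6% |
| 0.368 | 0.5 | 0.184 | 0.0637 | 0.2226 | 0.1309 | 0.2951 | 0.00834 + 0.02914 + 0.01881 = 5.6% |
| 0.288 | 0.7 | 0.2016 | 0.1303 | 0.3162 | 0.1052 | 0.2658 | 0.01371 + 0.03328 + 0.03462 = 8.2% |
| 0.288 | 0.5 | 0.144 | 0.1303 | 0.3162 | 0.2112 | 0.3553 | 0.02752 + 0.06679 + 0.04629 = 14.1% |

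**Step 4: other mixes, same formula with m and 16−m.** Each cell runs from f = 0.7 to f = 0.5.

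| Mature patients (m) | True ORR 36.8% | True ORR 28.8% |
|---|---|---|
| 0 (all 16 on first scan only) | 5.6% to 17.8% | 13.7% to 30.7% |
| 3 | 3.8% to 10.2% | 10.6% to 21.0% |
| 6 | 2.6% to 5.6% | 8.2% to 14.1% |
| 9 | 1.7% to 3.0% | 6.2% to 9.2% |
| 16 (mature data) | 0.7% | 3.3% |

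**Step 5: how many could be mature.** Take the fastest calendar that Protocol 4.1.1 allows, with no extra DLT patients and no time for committee review. The 9 µg/kg cohort starts on days 0, 7 and 8. The 12 µg/kg cohort starts on days 29 (8 + 21), 36 and 37. The main cohort starts from day 58 (37 + 21). If patient 16 starts on day 58 and is scanned on day 100 (58 + 42), the first three patients have 92 to 100 days of follow-up and the next three have 63 to 71 days. So even then three patients are past week 12, provided safety-cohort patients are among the 16. Slower accrual raises m.

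**The case against.** A reader might infer that anyone who first responds at week 12 or later is counted as a failure, or that a first-scan response rate is what gets tested. The documents do not support that. The look waits for the last of the 16, so earlier patients can already have week-12 or later scans. What is tested is best response to date with mixed follow-up. For the same reason the m = 0 row is an outer bound, not the expected risk.

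Other points for the plan:
- **The boundary is lenient.** With mature data it stops a combination at the desired ORR only 0.7% of the time. The interval allows a one-sided 10% at the minimal ORR. With 6 mature patients, f = 0.7 stays within that (8.2%) but f = 0.5 does not (14.1%). With 9 mature, both do.
- **There is an opposite bias.** Final best response needs two determinations more than 4 weeks apart (SAP 5.5.3.1), while the interim numerator takes unconfirmed responses, some of which will not confirm. This stands as a partial offset that the documents give no means of sizing. It does nothing for patients who have not yet responded.
- **The stop may be less mechanical than its wording.** The IDMC makes a recommendation to the sponsor (Protocol 10.1.12), and other efficacy endpoints are supportive. That softens the consequence, but the futility text itself says the study will be discontinued.
- **f is unknown.** The documents hold no time-to-response data, so the size of the effect is conditional.

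These points limit the size of the problem. They do not supply the missing follow-up requirement.

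**Conclusion.** The point holds in this form: SAP 5.6.12 requires no follow-up beyond post-baseline tumor data, so late-enrolled patients with one scan who would first respond later count as non-responders against a rate defined on best response until progression. The direction of this effect is certain; its size is not.

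With 6 of 16 patients mature and f between 0.7 and 0.5, the chance of stopping at the desired ORR is about 4 to 8 times that with mature data (0.0258/0.0067 to 0.0563/0.0067). At the minimal ORR it is about 2.5 to 4.3 times (0.0816/0.0326 to 0.1406/0.0326). These ratios rest on assumed values of f and m, and on treating mature patients as having shown every response they will ever show. They leave out the offset from unconfirmed responses, so they overstate the net effect to some unknown degree.

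This goes beyond missing detail, because following the rule as written raises the risk of a false stop. It does not make the boundary wrong: fewer than 2 of 16 is correctly derived and can stay.

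**What to change.** In SAP 5.6.12, keep the boundary and add a maturity condition:
- The look is passed as soon as 2 responses are seen among the 16.
- If fewer than 2 are seen, futility is not concluded until each of the 16 has had the second scheduled assessment (week 12 ±2), or has had progression, death, next-line therapy, study withdrawal or another protocol reason that ends scanning (Protocol 8.1.3 also lists pregnancy and end of study).
- A missed or non-evaluable second scan is treated as reached when the week-12 window closes, so the look cannot stay open.
- State whether safety-cohort patients are among the 16. The efficacy population includes them (Protocol 9.5, SAP 2.3), but the IDMC is described as applying only to the main cohort (Protocol 10.1.12).

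**Cost.** SAP wording only; the scans are already scheduled. When fewer than 2 responses are seen, the decision waits about 6 weeks and some further patients may be enrolled. The documents give no accrual rate, so that number cannot be stated. First responses after the second scan would still be missed; the change narrows the gap and does not close it.
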